2.4.2 Prior, concomitant and post therapies

Data for study drug administration will be listed by study part, cohort and subject.

Concomitant medications will be summarized for the safety set in separate tabulations based on the coding dictionary used. Concomitant medications used during the treatment phase will be summarized by anatomical therapeutic chemical (ATC) class, and preferred term.

Concomitant medications and significant non-drug therapies will be summarized by study part, therapeutic class and preferred term for the SAF. Any medication given at least once between the day of first dose of actual study drug received and the last day of the study will be a concomitant medication, including those which were started pre-baseline and continued into the treatment period. Concomitant medication will be identified based on recorded or imputed start and end dates of medication taking.

Concomitant medication will be assigned to Part 3 if the start date of the medication is after/on the date of first visit for Part 3 (see section 2.1.1).

2.5 Analysis of the primary objective

The primary objective of Part 1 was analyzed in the Interim 3 CSR. This analysis will not be repeated here. Details of the planned analysis can be found in Appendices 5.4.

The primary objective of Part 2 is to evaluate the safety and tolerability of multiple doses of branaplam for 52 weeks in subjects with Type 1 SMA. The primary objective for Part 3 is to assess long-term safety and tolerability of extended oral/enteral, once a week branaplam treatment in patients with type 1 SMA who have had at least 52 weeks of treatment in either Part 1 or 2 study of this protocol. The analyses are described below in the safety section. All information obtained on adverse events will be displayed by initial and administered dose and subject.

2.6 Analysis of the key secondary objective

There is no key secondary objective for this study.

2.7 Analysis of secondary objectives

All efficacy analyses will be conducted using the full analysis set (FAS).

2.7.1 Secondary endpoint

The following efficacy endpoints will be summarized with appropriate descriptive tables over time by study part and in Parts 2 & 3, additionally by treatment group:

- CHOP INTEND infant motor total score
- Respiratory function assessments (respiratory rate, pulse oximetry, paradoxical breathing, breathing pattern [chest circumference measured during quiet breathing (sleep)])
- Growth measurements (body weight, head circumference, length and chest circumference)
- Ventilation status
- Preservation of oral feeding
- HINE motor total score

- Ability to sit without support at 12-months of treatment: This is part of the HINE, if a subject has the ITEM="Sitting" with Score 3 or 4 then they are considered as able to sit without support. See [Table 2-14](#) below.

For all continuous secondary endpoints, summary statistics for raw and change from baseline (when baseline is available), will be provided.

For the categorical secondary endpoints, frequencies and relative percentages will be reported.

Other secondary endpoints

- AUC and Cmax of branaplam

For PK analysis please refer to section 2.9.

A summary of the number of patients and relative frequencies of patients with and without tracheostomy at baseline, installed or removed during the study will be provided by part and cohort (for parts 2 & 3).

The number of patients who had a tracheostomy or permanent ventilation during the study and discontinued the study drug on/after the start of the event will be provided by part and cohort (for parts 2 & 3).

HINE-2 and the Motor and Speech Domains

The domains for the HINE-2 motor score are provided in [Table 2-14](#) below. If all subscores are "Did Not Test" (DNT) then the HINE Motor Total Score is missing. If at least one subscore is available, then any other DNT will be imputed as 0 in the sum for the HINE Motor Total Score derivation.

Note: HINE motor score information is available in two source datasets, MOT and QUE. Data from both datasets will be combined and used in the HINE data analysis.

Table 2-14 HINE-2 and the Motor and Speech Domains

Item	Score	Functional definitions and score						
		0	1	2	3	4	5	6
Head Control	Did Not Test	Unable to maintain upright	Wobbles	All the time upright				
Sitting	DNT	Cannot sit	Sits with support at hips	Sits with support (props)	Stable independent sit	Pivots (rotates)		
Ability to Kick (in supine)	DNT	Does not kick	Kicks horizontal, leg(s) do not lift	Upward (vertical)	Touches leg	Touches toes		
Rolling	DNT	Does not roll	Rolls to side (supine)	Rolls to side (prone)	Rolls prone to supine	Rolls supine to prone		

Crawling (from supine)	DNT	Does not lift head	Props on elbow	Supports weight on hand	Crawls flat on abdomen (commando crawl)	Crawls on hands and knees		
Standing	DNT	Does not support weight	Supports weight	Stands with support	Stands unaided			
Walking	DNT	Makes no attempt at walking	Bounces	Cruises (holding on)	Takes a few steps	Walks independently (>10 steps)		
Hip strength	DNT	Unable to flex hips	Briefly flexes hip against gravity	Maintains hip flexion against gravity				
Speech	DNT/Can-not assess	Weak cry (cannot be heard outside of room with closed door)	Loud cry (can be heard outside of room with closed door)	Coos	Babbles in a speech-like way and uses many different sounds, including sounds that begin with p, b, and m	Babbles using long and short groups of sounds (tata, upup, bibibi)	Imitates different speech sounds	Says one word
Voluntary grasp	DNT	No grasp	Uses whole hand (rake)	Index finger and thumb but immature grasp	Pincer grasp			
Upper extremity function	DNT	Spontaneous movement of arm(s)	Hand(s) to midline on chest	Arm(s) held above head	Hand(s) to mouth	Arm(s) reach over body (supine)	Arm(s) reach over head (held upright)	

Feeding Status

Feeding status over the course of each part will be categorized as follows:

- Only exclusively tube fed
- Only orally fed
- Started on tube fed, switched to orally fed
- Started on orally fed, switched to tube fed
- Other (mixture of both tube and oral feeding)

Ventilation status

Permanent ventilation is included in a composite endpoint with death, permanent ventilation or tracheostomy (see Sections 2.7.2 and 2.8.3). A timeline of ventilation status is described below.

A patient's ventilation information might be recorded in several records (for e.g if the number of hours/day changes). Information should be combined. If two records are available for the same day with different number of hours per day, the maximum will be assumed.

Further Analyses

Additionally, the following analyses will be carried out:

- CHOP INTEND
 - Spaghetti plots of Total Score and Total Score Change from Baseline (Parts 1 & 3)
 - Spaghetti plots of Total Score and Total Score Change from Baseline stratified by treatment group (Parts 2 & 3)
 - Panel plots of individual CHOP INTEND Total Score and Total Score Change from Baseline – in each panel a spaghetti plot of all subjects (Parts 1 & 3, and 2 & 3)
 - Panel plots of individual Total Score Change from Baseline by time with dose as background shading – one panel per subject (Parts 1 & 3)
 - Stratified bar chart of subjects showing ≥ 4 improvement from baseline in Total Score by Baseline Age Group, and Time (Parts 1 & 3, and 2 & 3)
 - Table of Median Change in Total Score from Baseline by Visit and Baseline Age Group (Parts 1 & 3, and 2 & 3)
 - Table of subjects reaching Total Score ≥ 40 by Visit (Parts 1 & 3, and 2 & 3)
- Growth measurements
 - Spaghetti plots (growth curves) of length and weight versus age at evaluation by sex with CDC percentiles (Parts 1 & 3, and 2 & 3)
 - Summaries of chest circumference measured at the end of both inspiration and expiration during quiet breathing (sleep) by treatment group and part
- Feeding and Ventilation Status
 - Time lines of feeding and ventilation status with dose as background shading (Parts 1 & 3, and 2 & 3)
- HINE Motor Score and Items
 - HINE sub-scales Crawling, Head Control, Kicking, Rolling, Sitting, Standing, and Walking
 - Stacked bar chart by visit and part (Parts 1 & 3, and 2 & 3)
 - Table of milestones reached

HINE sub-scale	Milestone
Head control	Wobbles or all the time upright
Kicking	Any kick
Rolling	Any roll

Sitting	Stable independent sit or Pivots (rotates)
Crawling	Lifts head in any way (Props on elbow)
Standing	Supports weight
Walking	Makes any attempt (ie Bounces)

- HINE Motor Total Score
 - Table of frequencies of the following change from baseline categories by visit (Parts 2 & 3):
 - 1 = Worsening (<0)
 - 2 = No change (=0)
 - 3 = Improvement of 1 point
 - 4 = Improvement of 2 points
 - 5 = Improvement of > 2 points
 - Table of frequencies of subjects reaching a post-baseline score of ≥ 3 by visit (Parts 1 & 3, and 2 & 3)
 - Panel plot of individual values by time with dose as background shading (Parts 1 & 3 and 2 & 3)
 - Panel plot of individual values – in each panel a spaghetti plot of all subjects (Parts 2 & 3)
- Motor and Speech Performance
 - Hip Strength, Speech, Upper Extremity Function, and Voluntary Grasp
 - Stacked bar chart by visit (Parts 1 & 3, and 2 & 3)

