3.4 Rationale for study design

Due to the life-threatening severity of the disease, rapid clinical decline of these patients and the presence of effective therapy, that is also available in some European countries, it would be unethical to include a placebo treatment as part of the study design. Therefore, the proposed study design is an open label study with all patients on active treatment for the duration of the study. At the time of initiation of Part 1 based on the natural history over 13 weeks (about 3 months) in infants with type I SMA who have 2 copies of SMN2 and who are greater than 1 and less than 8 months of age, the following was agreed as a consensus: if symptomatic, no infant will hold their head up independently, or roll, sit, crawl, stand, or show antigravity leg strength. In addition, all infants will essentially lose proximal motor strength in all 4 limbs by 12 months of age (depends on how old they are when they enroll).

At the time of initiation of Part 2 additional sham control data are available: in symptomatic SMA Type 1 infants with onset of signs less than 6 months of age who have exactly 2 copies of SMN2 and who are at least 30 days and less than 180 days old, approximately 75% will be unable to maintain their head upright or kick horizontally, and almost all will be unable to complete any motor tasks in the HINE for rolling or sitting. No patients are expected to be able to crawl, stand or walk, and no acquisition of these skills is anticipated.

Type 1 SMA infants have severely impaired motor milestones indicating their motor neurons are dysfunctional and likely dying by the time of diagnosis, usually after 3 months of age. Thus, early treatment is vital if SMN protein elevation from splice modulation is to have any benefit.

Protocol No. CLMI070X2201

Based on the available information to date, Novartis assumes that SMN2 splice modulation will not lead to generating new motor neurons, but it should enable the survival and recovery of existing dysfunctional ones.

The study population (Type 1 SMA) was initially selected because, given the cell cycle arrest liability of branaplam and thus narrow therapeutic window, it was not considered appropriate to expose healthy adult volunteers who could not benefit from the study drug. An additional consideration was the inability of an adult first-in-human study to adequately predict bioavailability of the drug in a young infant population in this Type 1 SMA infant study.

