4.1 Inclusion criteria

4.1.1 Part 1

Screening	Baseline	Criteria
Х		 Written informed consent must be obtained from the parent / guardian before any assessment is performed.

Screening	Baseline	Criteria
х		 Type 1 SMA, diagnosed clinically, with symptom onset <6 months of age and genetic confirmation of mutations in both alleles of the SMN1 gene, and with SMN2 copy number of 2.
Χ		3. Best supportive care in place and stable for at least 14 days before screening.
Χ		4. Age at screening between 1 and 7 months
Χ	Х	5. Must be able to demonstrate antigravity strength in both biceps.
Х	х	6. Must have or agree to have placement of feeding tube for enteral access via nasogastric (NG), nasojejunal (NJ), percutaneous gastrostomy (PEG), or percutaneous jejunostomy (PEJ) tube for dosing LMI070 (Part 1 only and for patients who cannot be administered orally; tube may be removed between doses)
Х	х	 Medical care meets and is expected to continue to meet guidelines set out in the Consensus Statement for Standard of Care in SMA (Wang et al 2007), in the opinion of the Site Investigator.
Χ		8. At birth gestational age >32 weeks and body weight at birth >2 kg.
Х	Х	9. Must live within 2 hours drive of study center. Clearance should be obtained from the site investigator and sponsor if the patient resides more than 2 hours ground travel from the study center.
Х	Х	 Able to complete all study procedures, measurements and visits; and parent or guardian/patient has adequately supportive psychosocial circumstances, in the opinion of the Site Investigator.

4.1.2 Part 2

 7. I.Z		art 2
Screening	Baseline	Criteria
х		Written informed consent must be obtained from the parent / guardian before any assessment is performed.
X		2. Type 1 SMA, diagnosed with genetic confirmation of mutations in both alleles of the SMN1 gene, and with SMN2 copy number of 2.
Х		3. Best supportive care in place and stable for at least 14 days before screening as assessed by the investigator.
Χ		4. Age at screening up to 180 days of age
Χ	Χ	5. Must be able to demonstrate antigravity strength in both biceps.
x	x	6. Must have or agree to have placement of feeding tube for enteral access via nasogastric (NG), nasojejunal (NJ), percutaneous gastrostomy (PEG), or percutaneous jejunostomy (PEJ) tube for dosing branaplam (for the first administration only and for patients who cannot be administered orally; tube may be removed between doses)
	Χ	7. Minimum CHOP INTEND score of 15 at baseline

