2.1.1 General definitions

‘**Actual dose**’ will be derived as the current dose for each subject on a daily basis across the entire study; in the case of the day of a dose change, the new dose will be used.

‘**Treatment group**’ in Parts 2 & 3 will refer to the treatment group combination (as mentioned above) for efficacy analyses, and to the actual treatment for safety analyses (see definition below). In Parts 1 & 3, this will be Overall.

‘**Cohort**’ will refer to the initial dose for baseline or demographic characteristics.

The term ‘**Study Day**’ in this document relates to the Analysis Relative Day, Relative Start Day or Relative End Day as applicable. ‘**Study Day**’ is defined relative to the analysis reference date, which is the date of treatment assignment; it is the number of days from the reference date to the analysis date. For all dates on or after the analysis reference date, the study day is the difference to the analysis reference date plus one day (i.e. for date \geq reference date, study day = date - reference date + 1); for any dates prior to the analysis reference date, the study day is

simply the difference to the reference date (i.e. for date < reference date, study day = date - reference date). Thus, the Subject Reference Start Date is designated as Study Day 1, while the date directly prior to the reference date is defined as Study Day -1 (there is no Study Day 0).

'Baseline' is the last non-missing assessment obtained prior to the first administration of study drug. That means that if the measurement at the baseline visit is missing, then the previous measurement preceding baseline will be used as the baseline measurement. For pulse and blood pressure vital sign values, the baseline is the last non-missing value taken prior to the first administration of study drug.

'Treatment phase' includes the time interval on treatment and post-treatment follow-up. Any measurements taken after baseline will be considered as post-baseline measurements.

'Actual treatment' is defined as the treatment group the patient has most exposure to in each Part (for Parts 2 & 3), leading to a treatment group combination; in the case of two treatments having identical exposure, the higher dose will be used. This will be used for safety analyses.

'Calendar age' is defined as the age at the date of evaluation.

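### The HINE and CHOP INTEND threshold tables carry no baseline condition, so they pool children already at the threshold before the first dose with children who newly attain it

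*SAP*

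**What the plan says.** Under Further Analyses, SAP 2.7.1 lists three tables that count children at or above a fixed threshold:

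- HINE motor total: "Table of frequencies of subjects reaching a post-baseline score of ≥ 3 by visit (Parts 1 & 3, and 2 & 3").
- HINE items: "Table of milestones reached", covering seven sub-scales. Head control is met by "Wobbles or all the time upright", and kicking by any kick at all. Against the HINE-2 scoring table in the same section, six of the seven cut-offs sit at the lowest non-zero score. Only sitting asks for more (score 3 or 4).
- CHOP INTEND: "Table of subjects reaching Total Score ≥ 40 by Visit (Parts 1 & 3, and 2 & 3").

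No baseline condition is attached to any of them. SAP 2.7 puts all efficacy analyses on the full analysis set, which is every enrolled child who received a dose. SAP 2.1.1 uses the term post-baseline for timing only: "Any measurements taken after baseline will be considered as post-baseline measurements".

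On who may enter, Protocol 4.1.2 sets "Minimum CHOP INTEND score of 15 at baseline" for Part 2 and gives no upper limit. It also omits the symptom-onset requirement that 4.1.1 applies in Part 1.

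On scheduling, Protocol Table 7-3 has both HINE and CHOP INTEND at the Part 2 baseline. Table 7-1 has CHOP INTEND but no HINE at the Part 1 baseline, and the first Part 1 HINE window in SAP Table 2-2 is Week 19.

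**The concern.** To say that a child reached a milestone normally implies that the child could not do it before. These tables do not check that. A child who wobbles the head or kicks horizontally at baseline, and still does so at the first post-baseline visit, is counted alongside a child who gained the skill.

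There is no concurrent untreated group, and Protocol 3.6 leaves room for comparison with natural history, so a reader will tend to take such counts as gains. Protocol 3.8 already argues in this style, citing seven patients whose CHOP INTEND passed 36.

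The comparison of the two Part 2 doses is exposed as well. The cohorts were opened one after the other. The repeated-measures model in Protocol 11.5.1, which had terms for baseline value and baseline age category, is dropped in SAP section 4. A difference in starting ability between cohorts would therefore pass straight into these tables.

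**Working it through.** The plan states no figure for these tables, so there is nothing to reproduce. The check has four steps.

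**1. Literal reading.** A child with head control at score 1 at baseline and score 1 at Week 6 meets the item milestone. A child whose head is always upright (2) and who kicks horizontally (1) has a HINE total of 2 + 1 = 3 at baseline. If nothing changes, that child appears in the table of totals of 3 or more at every visit.

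**2. Is baseline attainment realistic?** Protocol 3.4 reports sham-control data in symptomatic infants aged 30 to under 180 days: "approximately 75% will be unable to maintain their head upright or kick horizontally". The complement is 100% - 75% = 25%. Being unable to hold the head up is score 0 on head control, and a horizontal kick is score 1 on kicking, so this statement lines up with the SAP's cut-offs for these two items. For rolling and sitting the same section says "almost all will be unable to complete any motor tasks in the HINE for rolling or sitting", so overlap there should be close to nil. It gives nothing for CHOP INTEND of 40 or more or for HINE total of 3 or more.

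**3. Effect on the counts.** Let b be the share at the threshold at baseline who keep it, and r the rate of new attainment among the rest. Then

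share shown = b + (1 - b) × r.

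The value of b is an assumption: 0.25 from step 2, with a range of 0.05 to 0.40. N = 25 is the Part 2 enrolment.

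| b | r | Share shown | New, of all children | New, of those below at baseline |
|---|---|---|---|---|
| 0 | 0.20 | 0.20 | 0.20 | 0.20 |
| 0.10 | 0 | 0.10 | 0 | 0 |
| 0.25 | 0 | 0.25 | 0 | 0 |
| 0.25 | 0.20 | 0.25 + 0.75 × 0.20 = 0.40 | 0.75 × 0.20 = 0.15 | 0.20 |
| 0.40 | 0 | 0.40 | 0 | 0 |

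With r = 0 and b = 0.25, the expected count is 25 × 0.25 = 6.25 children (central 95% binomial range 2 to 11). The chance of at least one is 1 - 0.75^25 = 0.999. For b of 0.05, 0.10 and 0.40 the expected counts are 1.25, 2.5 and 10. Counting only children below the threshold at baseline gives 0 in every case. With b = 0 the two ways of counting agree.

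For the dose comparison, assumed baseline shares of 10% in one cohort and 40% in the other, with no new attainment in either, would show 10% against 40%.

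**4. What other outputs cover.**

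- CHOP INTEND: change from baseline, improvement of 4 or more points, and median change by baseline age group. Partly covered in both pairings of parts.
- HINE total, Parts 2 & 3: change-from-baseline categories. Partly covered.
- HINE total, Parts 1 & 3: no change categories, and no scheduled pre-dose HINE. Not covered.
- HINE items: no output is set against baseline, and the first stacked-bar bin in SAP Table 2-15 begins after baseline. Not covered in any part.

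**The case against.** The SAP is silent rather than explicit. It does not tell the programmer to count children already at the threshold, and the word reaching could be coded as new attainment. That is fair, but it is also the reason to write the rule down. Nothing in the text would stop the pooled count.

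The tables are descriptive, sit under Further Analyses and belong to a study that both documents call non-confirmatory. There is no key secondary objective, and no error rate is touched. Absolute status by visit is also a legitimate display where natural-history comparison is foreseen. All of this stands, and it limits the weight of the point.

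The 25% is soft. It is the complement of one joint phrase and does not clearly give a rate for each item. It describes infants under 180 days, whereas the tables run through Week 52 and Part 3. Protocol 3.4 also records the consensus that proximal limb strength is essentially lost by 12 months. Keeping an early skill may therefore itself be a benefit, particularly at later visits. This stands too: the fault is that maintained and newly gained skills share one label, not that maintained skills have no value.

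A baseline CHOP INTEND of 40 or more should be uncommon in symptomatic infants, since Protocol 3.8 treats scores above 36 as exceeding historical controls. The missing ceiling shows that it is possible, not that it is frequent.

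For Part 1, the absence of HINE from the baseline schedule does not prove that no pre-dose record exists. The Amendment 6 summary says milestone information had been collected at the investigator's discretion, and SAP 2.7.1 combines two HINE source datasets.

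**Conclusion.** The point holds as a defect in how three descriptive tables are defined. Followed as written, they pool prior ability with new attainment. The effect is likely largest for head control and kicking, where up to roughly a quarter of children may qualify at baseline. That is about 6 of 25 in Part 2, if the sham-control share applies, the skill is kept and nothing new is gained. Over the assumed range of 5% to 40% the figure runs from 1.25 to 10 children. It should be near nil for rolling and independent sitting, and it cannot be sized for HINE total of 3 or more or CHOP INTEND of 40 or more. No baseline distribution is given for this trial, so all of these counts are illustrations.

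A reader might go further and infer that the plan presents natural ability as an effect of the drug, or that these counts carry the efficacy case. The documents do not support that. They nowhere call the counts achievement on treatment, change-from-baseline outputs stand beside them, and the efficacy reason given for the Part 3 dose in Protocol 3.5.3 is change in HINE-2 score. Nor do they establish that new attainment on HINE can never be shown in Part 1. They show only that no pre-dose HINE was scheduled.

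**What to change.** In SAP 2.7.1, for Parts 2 & 3 on all three tables, and for Parts 1 & 3 on CHOP INTEND:

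- add the number and percentage meeting each threshold at baseline;
- report *newly reached* with children below the threshold at baseline as the denominator;
- report *maintained* separately among those who met it at baseline.

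For HINE in Parts 1 & 3, label the tables *present at visit* unless a usable pre-dose record is found in the source datasets, and footnote that no baseline HINE was scheduled.

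The SAP already works this way elsewhere: tracheostomy is split into present at baseline, installed and removed, and feeding status is classified by where the child started. The cost is a baseline flag from assessments already scheduled, a few extra table columns and a little more programming. No new data are needed. The counts of children who reached a threshold will look less favourable.
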